RESEARCH PROTOCOL OUTLINE

Title of Project: Mobile Health Study and Enhanced Symptom Monitoring to Prevent Severe Illness from COVID-19 in Cancer Patients

Principal Investigators: [name]., Department of OB/GYN
[name], Dept. of Family and Preventive Medicine

Co-Investigators: [name], College of Public Health

Abstract

The severe acute respiratory syndrome corona virus 2 (SARS-CoV-2) outbreak in late 2019 has resulted in over 4.28 million confirmed cases of novel coronavirus disease (COVID-19), with over 292,000 confirmed deaths worldwide (as of May 13, 2020). Severe disease occurs in ~10% of cases overall. However, risk for severe disease and mortality is greater in immunocompromised cancer patients, requiring scarce ventilation resources and intensive care unit space to address rapid clinical deterioration in this population. We propose to use the established Insight™ mHealth Platform, a component of the Stephenson Cancer Center (SCC) mHealth Shared Resource, to create the “Symptom Tracker” app. The Symptom Tracker (Insight™) app will enable real-time monitoring of cancer patient symptoms that are consistent with early signs of SARS-CoV-2 infection in this high-risk population by automatically (and securely) transferring this information to health care providers. The primary aim of this study is to determine the feasibility, ease of use, and perceived utility of this app to monitor symptoms and health risk behaviors among cancer patients currently receiving chemotherapy. Health risk behaviors, standard COVID-19 screening questions, and a single chemotherapy risk question will be assessed daily through the smartphone app. Specific responses will automatically trigger an alert to clinic nurses AND provide app-based access to contact the clinic for triage to home care or emergency assessment. When/if study participants screen positive for COVID-19, they will receive a device to measure their pulse and blood oxygen levels daily. This information and COVID-19 symptoms will be monitored daily via the Symptom Tracker (Insight™) app. This study will determine if an app can be used to rapidly report COVID-19 symptoms and quickly intervene to reduce morbidity and mortality in immunocompromised cancer patients. Further, data from this study will be used to inform the development of future mHealth interventions that will be tested in fully powered randomized control trials.

A. Specific Aims

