The primary objective of this research is to use innovative mHealth technology to monitor symptoms in real-time and facilitate medical triage of high-risk patients. The current study will obtain data on the feasibility of an innovative mHealth application to track symptoms and automatically intervene upon reported high-risk symptoms among cancer patients who are receiving cytotoxic chemotherapy or immunotherapy treatments. This objective will be attained by pursuing the following specific aims:

1. Determine the feasibility, ease of use, and perceived utility of the Symptom Tracker (Insight™) mHealth app to monitor symptoms and health risk behaviors for up to 500 patients who are receiving chemotherapy to treat cancer.
 - a. On average, participants will complete >50% of all prompted daily phone based ecological momentary assessments (EMAs).

- b. Most participants will report that the app is easy to use, and provides useful information (assessed quantitatively and qualitatively during the 24-week phone based or RedCap follow-up interview).
2. Examine participant characteristics and outcomes of those who do and do not test positive for COVID-19 during the 24-week monitoring period.
 - a. Among those who undergo enhanced monitoring, we will use descriptive statistics to summarize the proportion of patients experiencing the following outcomes: manifestations of severe disease, treatment related toxicity, need for hospitalization, and SARS-CoV-2 related mortality.
 - b. We will also compare outcomes and tolerability of enhanced self-monitoring for severe infection and compare rates of disease related morbidity and mortality to baseline rates published in the literature.
 - c. We will use quantitative and qualitative methods to evaluate participant satisfaction with the app among those who test positive for COVID-19 and are asked to report vital signs each day.
3. Collaboratively document and share lessons learned regarding the impact of the COVID-19 pandemic on cancer care delivery via telemedicine and mHealth technology. We commit to a collegial collaboration with other cancer centers funded to study the use of telemedicine through the COVID-19 CCSG supplement mechanism.

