This study will also explore the potential reduction of severe COVID-19 mediated disease through: 1) reducing time from symptom detection to treatment initiation (i.e., comparing treatment initiation times among those who test positive for COVID-19 in this study to published literature), and 2) closely monitoring COVID-19 symptoms among those who contract the virus (i.e., again, comparing participants in this study to published literature). COVID-19 is a novel virus and we do not fully understand its impact on our patient population. This study will provide useful, granular information about the daily symptoms of and recovery from COVID-19 in cancer patients. Data from this study will be used to pursue NIH R01 funding to formally evaluate the effects of using mHealth technology to monitor symptoms and health risk factors and intervene in real-time.

B. Background and Significance

The severe acute respiratory syndrome corona virus 2 (SARS-CoV-2) outbreak in late 2019 has resulted in approximately 4.28 million confirmed cases of novel coronavirus disease (COVID-19), with over 292,000 confirmed deaths worldwide (as of May 13, 2020)[1]. The United States has reported the greatest number of cases across the world, with a total of 1.4 million new cases and over 83,000 attributable deaths as of May 13, 2020. Severe disease accounts for approximately 10% of cases and adds tremendous burden on limited medical resources and medical personnel.

Risk factors for severe disease are largely unknown, but clinical experience suggests that persons over age 65 with co-morbid conditions, such as immunosuppression from cancer or chemotherapy, place cancer patients in the “high-risk” group for severe manifestations of COVID-19 mediated disease [2]. Therefore, cancer patients are likely at increased risk for COVID-19 infection and may have a poorer prognosis. According to recent data, the risk of severe infection in cancer patients approaches 40% with up to a 20% mortality rate [3]. Thus, there is increased need for invasive ventilation and intensive care unit admission to circumvent rapid clinical deterioration in this population. Novel methods are needed to remotely monitor for SARS-CoV-2 infection and rapidly intervene to reduce morbidity and mortality in cancer patients exhibiting symptoms of the virus. Given evidence of poor outcomes in cancer patients, early intervention may significantly improve outcomes.

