Aim 2. We will examine participant characteristics among those who are and are not transitioned to an Aim 2 monitoring of vital signs and severity of COVID-19 symptoms. We will also examine participant characteristics and outcomes for those that require emergent intervention versus non-emergent intervention. Among those who undergo enhanced monitoring, we will use descriptive statistics to summarize the proportion of patients experiencing the following outcomes: manifestations of severe disease, treatment related toxicity, need for hospitalization, and COVID-19 related mortality. We will also compare outcomes and tolerability of enhanced self-monitoring for severe infection and compare rates of disease related morbidity and mortality to baseline rates published in the literature. We will evaluate participant satisfaction with the app and identify ways to improve this novel patient monitoring technology. We will perform logistic regression to determine the odds of experiencing primary outcomes, based upon baseline characteristics (e.g., sex, race/ethnicity, cancer stage/type). Kaplan-Meier survival curves and log-rank tests of homogeneity will be used to identify the survival functions, describing the time to resolution of symptoms based upon

demographic characteristics. Because COVID-19 is a novel virus and we do not fully understand its impact on our patient population, this study will provide useful, granular information about the daily symptoms of and recovery from COVID-19 in cancer patients.

Aim 3. No analyses proposed, as this is a collaboration aim.

N. Data and Safety Monitoring Plan

Data quality and integrity will be held to the highest standard to ensure accurate reporting and documentation of the objectives outlined in the proposal. The Institutional Review Board and the Office of Clinical Research will monitor data and safety monitoring. The institutional plan for data and safety monitoring for all trials funded by the NCI has been adopted by the University and will be utilized for conduct of our planned proposal.

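### Aim 2 takes COVID-19 outcomes from enhanced-monitoring entrants, a set that can omit the infected patients sickest at triage and so favour the study against published rates

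*Combined protocol and SAP*

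**What the plan says.** Aim 2 (section A) is framed by test status: "Examine participant characteristics and outcomes of those who do and do not test positive for COVID-19 during the 24-week monitoring period". Aim 2a and section M, in the same words, then take the outcome proportions from a different group: "Among those who undergo enhanced monitoring, we will use descriptive statistics to summarize the proportion of patients experiencing the following outcomes". The outcomes are severe disease, treatment toxicity, hospitalization and COVID-19 mortality. Aim 2b and section M go on to "compare rates of disease related morbidity and mortality to baseline rates published in the literature", in a sentence that gives no denominator. Section M also plans a further contrast: "We will also examine participant characteristics and outcomes for those that require emergent intervention versus non-emergent intervention".

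Entry to enhanced monitoring is described in several places:

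- **Abstract:** "When/if study participants screen positive for COVID-19, they will receive a device to measure their pulse and blood oxygen levels daily". The same section uses the word screening for app items: "standard COVID-19 screening questions, and a single chemotherapy risk question will be assessed daily through the smartphone app".
- **Section D, Study Design and Study application:** people who screen positive are triaged. Those judged non-emergent receive the oximeter and begin the enhanced period.
- **Section D, EMA text after Table 1:** a participant who contracts COVID-19 presses the COVID-19 Positive button, which switches the app to enhanced questions for 21 days. No triage limit and no verification step are stated.

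Other text points to a tested population. Aim 2c speaks of satisfaction "among those who test positive for COVID-19 and are asked to report vital signs each day", and the exploratory text in section A plans "comparing treatment initiation times among those who test positive for COVID-19 in this study to published literature".

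On data, the 16 chart-review items (a to p) in section E include no COVID-19 test. Study application separately plans extraction of COVID-19 data from the health record, and section E refers to an Appendix for the full list. That Appendix is not in the text reviewed.

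**The concern.** Section D (Study Design) hypothesizes that monitoring will improve COVID-19 morbidity and mortality relative to published rates. There is no control arm, so that comparison is the only evidence on the hypothesis. The severity and mortality figures for cancer patients given in section B come from a reference on cancer patients with SARS-CoV-2 infection, and nothing in the protocol limits that reference to non-emergent cases.

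If the study side consists mainly of patients judged non-emergent at triage, it starts with a better prognosis than an unselected infected group. Its severe-disease and mortality proportions would be lower even if monitoring did nothing. Uninfected entrants, if there are any, act in the same direction on severe COVID-19 and COVID-19 death, because they cannot have either. Hospitalization and treatment toxicity are different: both occur in uninfected patients on chemotherapy and need not be diluted.

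The data are meant to support a later grant application, so a favourable comparison produced by selection would matter there.

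**Working it through.** The plan gives no sample size, error rate or expected number of infections for Aim 2, so there is no figure to reproduce. The check has two parts.

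**Who is in the set**

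| Question | Text | Implication |
|---|---|---|
| Are emergent cases in? | Study Design and Study application: non-emergent only | Sickest at triage left out |
| | Button text: no triage limit | Some may still enter |
| | Study application: hospitalized patients may continue daily entries | Deterioration after entry is kept |
| Are entrants infected? | Aim 2c, Study Design, button text | Infection intended |
| | No visible rule requiring a documented test | Not guaranteed |

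**How far the proportions could move**

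Inputs:

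- r, the rate among all test-positive participants: 40% severe and 20% mortality (section B). These are background figures and not a named comparator. They serve here as the rates that would hold with no monitoring effect.
- e, the share of test-positive participants triaged as emergent who never enter: not in the documents; assumed 0 to 20%.
- r_E, the rate in those patients: not in the documents; assumed 80% severe and 50% mortality.
- s, the infected share among entrants: not in the documents; assumed 50% to 100%.

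*Leaving out emergent cases.* Rate in the remaining confirmed entrants = (r − e × r_E) / (1 − e).

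| e | Severe | Mortality |
|---|---|---|
| 0 | 40% | 20% |
| 10% | (0.40 − 0.08)/0.90 = 35.6% | (0.20 − 0.05)/0.90 = 16.7% |
| 20% | (0.40 − 0.16)/0.80 = 30% | (0.20 − 0.10)/0.80 = 12.5% |

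If emergent patients fared no worse than the rest (r_E = r), nothing would change.

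*Uninfected entrants, taken alone.* Observed proportion = s × r, so the relative fall is 1 − s whatever r is.

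| s | 100% | 95% | 90% | 75% | 50% |
|---|---|---|---|---|---|
| Severe, r = 40% | 40% | 38% | 36% | 30% | 20% |
| Mortality, r = 20% | 20% | 19% | 18% | 15% | 10% |

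*Both together, in assumed counts with no effect of monitoring.*

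1. All test-positive: 50 patients, 20 severe (40%), 10 deaths (20%).
2. Ten are triaged as emergent and never enter, with 8 severe and 5 deaths. The 40 confirmed entrants show (20 − 8)/40 = 30% severe and (10 − 5)/40 = 12.5% mortality.
3. Ten uninfected entrants are added: 12/50 = 24% and 5/50 = 10%.

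Taken in this order, the 16-point severity gap (40 − 24) is 10 points from omission and 6 from dilution. The 10-point mortality gap (20 − 10) is 7.5 and 2.5. The all-test-positive set returns 40% and 20%, and it also holds 50 patients.

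**The case against.** The strongest reply is that the plan clearly means infected patients. The button text is conditional on contracting COVID-19. Sections K and P distinguish being at high risk from having contracted the virus. A symptom flag leads only to staff contact, and staff supply the oximeter. Aim 2c treats those reporting vital signs as having tested positive. A reader might infer that the set is filled by people who merely answered symptom questions positively; the documents do not support that. Nor do they support saying that test results will go uncollected. COVID-19 data extraction is planned, the Appendix may list the test, and items a to p also omit the Aim 2a outcomes, so they cannot be the whole record extraction. This largely answers the dilution point: what stands is only that no visible rule makes the analysed set equal the test-positive set.

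A reader might also infer that emergent patients are certainly excluded. That goes too far, because the button has no triage limit. Section M's emergent versus non-emergent contrast shows that outcomes in emergent patients will be looked at. It does not, however, bring those patients into the comparison with published rates, so the omission point stands even if every entrant is infected.

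It is also fair that the study is a feasibility study, that Aim 2a is descriptive, that no test against a literature rate is specified, and that an uncontrolled comparison cannot show benefit under any denominator. This limits the severity. It does not justify leaving in a selection that can be removed with a definition.

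**Conclusion.** The concern holds for the literature comparison in Aim 2b and section M. As written, the most natural denominator is enhanced-monitoring entrants. That set can omit infected patients who were sickest at triage, which favours the study's hypothesis. Possible dilution by uninfected entrants is secondary and may be zero.

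The direction of the omission effect rests on two assumptions: that some emergent cases do not enter, and that they fare worse than the rest. The direction of dilution for COVID-19 death rests on correct attribution of deaths. The size cannot be fixed from the documents. Every shift shown above depends on assumed shares or counts, and 40% and 20% would not be the expected rates for a purely non-emergent group.

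A reader might infer that section M contradicts the aims or that the trial's main result is compromised. Neither follows: section M repeats Aim 2a, and the primary feasibility aim does not use this set. Severity is minor to moderate.

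**What to change.** In section M:

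1. Base the comparison with published rates on all participants with a documented positive SARS-CoV-2 test during the 24 weeks, including those triaged as emergent.
2. Show the enhanced-monitoring entrants with a documented test alongside, and unconfirmed entrants as a separate group.
3. Keep tolerability of monitoring on all entrants, and leave the clinical trigger for starting it unchanged.

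Take test result and date from the COVID-19 record extraction already planned in Study application, adding these two fields only if the Appendix does not already list them. Allow outside test reports to be entered in REDCap.

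The cost is a short set of definitions and at most two fields for up to 500 participants. Some outside reports will have to be obtained. Infections that were never tested, possibly milder ones, leave the main comparison, which could raise its rates somewhat; showing unconfirmed entrants separately makes part of that visible. The comparison set need not shrink, because emergent test-positive patients join it.

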As a practicing oncologist within Stephenson Cancer Center, [name], Ph.D. is knowledgeable about the medical needs of the population that is being recruited for this study, and she regularly uses evidenced-based interventions to treat cancer. Her research and clinical experience complement [name] experience with research using mobile technology for health improvement. Additional study investigators include [name] (biostatistician) and [name] (basic and translational scientist) have agreed to assist with study recruitment and follow-up procedures.

D. Research Design and Methods

Study Design: A total of 500 treatment-seeking males and females will be asked to complete daily monitoring of symptoms and weekly monitoring of health risk factors weekly via smartphone app (Aim 1). Those who screen positive for COVID-19 will be triaged to emergency or non-emergency medical treatment. COVID-19 positive patients identified for non-emergent medical treatment will receive a study-supplied device to measure their oxygen level and heart rate and be instructed in the device's use. They will be prompted to enter vital signs data daily (such as body temperature, oxygen level, and heart rate) and questions from the app will change to assess the severity of COVID-19 related symptoms and inform changes in level of care, to emergency or non-emergency medical management as indicated by self-reporting. The proposed study will assess the impact of heightened symptom and vital sign monitoring on the early identification of severe manifestations of COVID-19 in this high-risk population (Aim 2). It is hypothesized that this will significantly improve COVID-19 related morbidity and mortality compared to the national and international rates currently reported in the literature. Figure 1 displays the participant flow through this 24-week study.

The SCC mHealth Shared Resource has created the versatile and reusable Insight™ mHealth Platform. Insight™ is HIPAA compliant and data are encrypted within the app. There will be 4 sources of data for the current study: 1) in-person data collected in a private room at the SCC

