When participants provide a pattern of responses that are suggestive of heightened risk for COVID-19 (See algorithm in Appendix), they will receive a suggestion to contact SCC staff, and the app will send an encrypted email containing this information to [name] and other SCC staff with a request to contact the participant to assess symptoms (see Appendix) and whether urgent medical attention is indicated. Should urgent medical attention be warranted, the patient will be instructed to the clinical unit most appropriate to the symptoms they reported through the app algorithm or discussed with the clinical nursing or physician staff. Non-emergent patients who screen positive for COVID-19 will begin an enhanced symptom and vital sign monitoring period that will continue until the participant reports that they are no longer symptomatic and/or a medical professional informs them that they no longer need to self-quarantine, which is expected to be approximately 21 days. These patients will receive a pulse oximeter (provided by the study) and the app questions will change to include daily prompts requesting that the patient input morning vital signs (temperature, heart rate, blood oxygen levels (SpO2)) and answer questions specific to the severity of symptoms and/or emergence of new symptoms of COVID-19. If a patient is hospitalized, they can continue to complete the daily assessments if they are willing and able to do so. The app will also support check-ins with SCC staff and after-hours medical staff as needed after diagnosis of COVID-19 or until the patient has been medically released from self-quarantine. Once the participants have completed the enhanced symptom and vital sign monitoring portion of the study, the pulse oximeter will be returned to the research team at the time of their next scheduled appointment. These devices will then be sterilized with both alcohol-based sanitizing products as well as ultraviolet light exposure in accordance with practices endorsed by the Centers for Disease Control.

Participants will continue to use the app to complete a final 24-week follow-up survey and will be contacted by phone (or RedCap if a medical condition prevents them from being able to speak for long periods of time) to complete a brief qualitative interview 24 weeks after study enrollment. Relevant demographic, cancer-specific and COVID-19 related data will be extracted

from electronic health records at the conclusion of the study.

E. Chart Review

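### Aim 2 sets severe disease against published rates, but the app helps detect and prompt it and the summarized group is selected, so the bias runs in an unknown direction

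*Combined protocol and SAP*

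**What the plan says.** Section M, Aim 2, gives descriptive proportions for "manifestations of severe disease, treatment related toxicity, need for hospitalization, and COVID-19 related mortality" among those who undergo enhanced monitoring. A following sentence, repeated from Aim 2b in section A, plans to compare outcomes and tolerability and to "compare rates of disease related morbidity and mortality to baseline rates published in the literature".

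Study Design in section D gives monitoring two purposes. It is to "assess the impact of heightened symptom and vital sign monitoring on the early identification of severe manifestations of COVID-19", and the result is expected to "significantly improve COVID-19 related morbidity and mortality compared to the national and international rates currently reported in the literature". The same paragraph lets self-reported answers move a patient between emergency and non-emergency management.

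Under Study application in section D:
- A worrying pattern of answers suggests that the patient contact staff, and sends staff a request to assess the patient.
- If urgent attention is needed, "the patient will be instructed to the clinical unit most appropriate to the symptoms they reported".
- Positive patients who are not emergent enter enhanced monitoring, with a study oximeter and daily oxygen saturation entry.

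Section D also says that the health record is used as needed to fill gaps or resolve discrepancies in outcomes collected through the app surveys. Section B quotes published risks in cancer patients of about 40% for severe infection and up to 20% for death. The supplied text does not define severe disease or morbidity.

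**The concern.** The app is both the intervention and part of the measuring instrument. One stated goal is the "early identification of severe manifestations of COVID-19 in this high-risk population", which tends to add recorded severe events. The next sentence expects less morbidity than in published cohorts, which are not described as using this app. Nothing in the supplied text separates an event that the app found or prompted from one that reflects the course of the disease.

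The group summarized is a second problem. If patients who need emergency care at diagnosis do not enter enhanced monitoring, the sickest positives are missing from the proportion, which tends to lower it.

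The two distortions pull in opposite directions and neither is measured. Section A says the data will support an application for further funding, so a rate on either side of 40% could be given a meaning it does not have.

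**Working it through.** **Inputs from the protocol.** Severe-disease benchmark p = 0.40 and mortality of up to 0.20 (section B). No published rate is quoted for hospitalization, ICU admission or ventilation. The plan gives no effect size, alpha, power or expected number of infections for this comparison, so it has no figure of its own to reproduce.

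**Assumed inputs, shown over ranges.**
- t: true severe rate with the app.
- r: share of the non-severe who are relabelled as severe through monitoring.
- e: share of positives who are emergent and outside enhanced monitoring, all taken as severe.
- RR: true effect of the app on severe disease.
- A: ascertainment ratio against the published cohorts.
- D: inflation of the denominator by extra mild cases.

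**1. Detection alone.** Observed rate = t + r(1 − t), with t = 0.30.
- r = 0.10: 0.30 + 0.10 × 0.70 = 0.37
- r = 0.20: 0.30 + 0.20 × 0.70 = 0.44
- Break-even with 0.40: r = (0.40 − 0.30)/0.70 = 0.143

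The true reduction shrinks at r = 0.10, and reverses only above 14.3% relabelling.

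**2. Selection alone, no app effect.** Observed rate = (p − e)/(1 − e).
- e = 0.05: 0.35/0.95 = 36.8%
- e = 0.10: 0.30/0.90 = 33.3%
- e = 0.20: 0.20/0.80 = 25.0%

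An app that does nothing would appear beneficial.

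**3. Effect, ascertainment and denominator.** Observed rate = p × RR × A/D.
- RR = 1, A = 1.25, D = 1: 0.40 × 1.25 = 50%, so no effect looks like harm.
- RR = 0.7, D = 1: 28% at A = 1.0, 35% at A = 1.25, 42% at A = 1.5. The rate passes 40% only if A > 1/0.7 = 1.43.
- RR = 0.7, D = 1.25: A must exceed 1.25/0.7 = 1.79. At A = 1.25 the rate is 28%.

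**4. Selection and ascertainment together, no app effect, A = 1.25.**
- e = 0.10: 0.333 × 1.25 = 41.7%
- e = 0.20: 0.25 × 1.25 = 31.2%

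The same ineffective app falls on either side of the benchmark, depending on a share that the plan does not state.

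**5. Consequence for a formal comparison.** Assume 50 of the 500 are infected and a one-sided exact test at 0.025 against 40%, which rejects at 12 or fewer events. Under a true 30% reduction, the chance of showing a rate below 40% is 0.33 at A = 1.0, 0.07 at A = 1.25 and 0.01 at A = 1.5.

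**The case against.** **Direction.** A reader might infer that a working app must raise severe disease and hospitalization. The documents do not support that. Section A expects the app to reduce severe disease, and step 3 shows that a 30% reduction is overturned only if ascertainment rises more than 1.43-fold. Extra mild cases and the non-emergent restriction both push the rate down.

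**Hospitalization.** A reader might also infer that the plan tests hospitalization against the literature. The four outcomes are listed as descriptive proportions, the comparison sentence does not name hospitalization, and no published hospitalization rate is quoted. Its inclusion under outcomes or morbidity is a fair reading, but not the text. Severe disease is the firmer case because its benchmark is quoted.

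**Mechanism.** Nothing says that a home saturation reading by itself counts as severe disease. Staff, not the app, are asked to judge urgency. How the published cohorts ascertained severity cannot be seen from here, and the alert algorithm and full chart-review list are in an appendix that was not supplied. The abstract, and the description of the app's COVID-19 positive button in section D, do not repeat the non-emergent restriction, so the selection may be weaker than Study application implies. These points limit what can be said about size. They do not remove the bias, because each is an unstated quantity on which its direction depends.

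**Weight.** The primary aim is feasibility, and reduction of severe disease is exploratory. That stands, but Study Design in section D still states a directional hypothesis.

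**Conclusion.** The concern holds as a bias of unknown direction. Under the plan as written, a severe-disease rate above or below about 40% cannot be read as harm or benefit. The same applies to hospitalization if it is included in the comparison. The illustrations span 37% to 44% for a true rate of 30%, and 25.0% to 36.8% for an app with no effect; these rest on the assumed r and e, not on figures in the protocol. Death is much less open to the detection problem, but it shares the denominator problem. Aim 1 is unaffected. This is worth correcting because the repair is cheap and the hypothesis in section D cannot be interpreted without it.

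**What to change.** In section M, Aim 2:

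1. Rest any claim of improvement over the literature on COVID-19 death, with invasive ventilation as supporting evidence. Section B already points to "increased need for invasive ventilation and intensive care unit admission" as the burden of concern. ICU admission is left out of the claim because it is also a care decision downstream of app triage. Ventilation needs a named published rate, since none is quoted.
2. Compare severe disease only if it is defined by health-record criteria matched to the published source, without counting home-oximeter readings alone.
3. Use all COVID-19 positives, including emergent ones, as the denominator for this comparison. Section M already plans to examine outcomes in emergent and non-emergent patients.
4. Report hospitalization, ICU admission and home-detected desaturation descriptively, split by whether an app alert came first, with no better-or-worse reading.

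**Cost.** Wording, fewer events and a wider interval. A few chart-review fields are also needed (admission date, ICU, ventilation, death): the section E list does not contain them, although Study application foresees extraction of COVID-19 data. Survey time stamps exist, but admission dates must be added to order events against alerts.

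**What remains.** Extra mild cases found by daily screening would still dilute even the death rate. At D = 1.25 (assumed), 20% becomes 0.20/1.25 = 16% with no effect, so the report should say so.
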